### Summary of Changes

Page #	Section	Reason for Change
Amendment 1 - July 26, 2021		
3	Model Convergence	Clarify handling of model convergence.
6	Modeling Treatment Heterogeneity	Additional use of Pennsylvania statewide variant data as a surrogate for patient-level variant data
November 4, 2021		
7	Appendix Read-out	Provided details of the final analytical read-out.

### Trial Design Introduction

This trial is a platform trial investigating the relative safety and efficacy of multiple monoclonal antibody (mAB) regimens for the treatment of COVID-19 illness. This document describes the statistical details for the trial investigating the relative efficacy of multiple mAB regimens for patients meeting the FDA emergency use authorization (EUA).

The trial randomly allocates which mAB regimen patients receive and will evaluate their comparative effectiveness. Adaptive randomization will be utilized where mAB arms that are performing better will be given higher randomization probabilities. Different mAB arms may be added during the course of the trial and different mAB strategies may be dropped for futility. For the primary analysis of patients within the FDA EUA, there will be no control arm and all arms will be directly compared to all other arms for relative efficacy.

### Treatment Arms

The trial may investigate multiple mAB strategy arms. Let  $k$  the number of active mAB strategies at any time in the trial. We label these arms as  $a=1, \dots, k$ .

### Primary Endpoint

The primary endpoint in the trial is hospital-free days (HFDs). The endpoint is a composite of death and number of days alive and free of the hospital. The worst outcome is that a patient dies within 28 days. This outcome is labeled as  $a-1$  HFDs. For patients who do not die within 28 days the primary endpoint is the number of days alive and free of hospitalization. For patients alive at day 28 the endpoint is characterized as an integer value with the number of days free of hospital admission, with possible

values 0, 1, 2, 3, ..., 28. For statistical analyses the endpoint is modeled as an ordered categorical variable. If a patient has intervening days free of hospital and then has a re-hospitalization the patient will be given credit for the intervening days as “free” of the hospital.

## Primary Analysis Population

The primary analysis population, used for all adaptive analyses is the “As-Infused” population. The intent-to-treat population includes all patients randomized to an mAB arm. The “as-infused” population includes those patients that show up and are infused for their mAB. Given that all arms are a mAB arm, there is no anticipated relationship between lack of infusion and the assigned arm. Hence all adaptive analyses and safety analyses will be based on the as-infused population (where patients are coded by the mAB arm they receive). Patients who receive a randomized mAB allocation and are not infused may be tracked as a real-world evidence arm of outcome for a non-mAB control (see secondary analyses).

## Primary Analysis Model

The primary analysis model for the primary endpoint is a cumulative proportional odds model. Let the probability of an outcome of less than or equal to  $y$  be  $\pi_y = \Pr(Y \leq y)$ . Let  $a$  be the indicator of treatment arm ( $a=1,\dots,k$ ). The model adjusts for the following baseline variables:

1. ED or infusion center (0=infusion center, 1=ED)
2. Age (with categories of <30, 30-39, 40-49, 50-59, 60-69, 70-79, and  $\geq 80$ ; 60-69 will be used as the referent)
3. Sex (sex at birth, male is the referent)
4. COVID-19 variant (0=unknown/uncollected (referent), categorical endpoint for each known variant)
5. Time (two-week epochs of time are used for adjustments; the most current 4-week period is the referent)

The primary analysis model is based on a cumulative logistic regression, where  $\pi_y = \Pr(Y \leq y)$ , where

$$\log\left(\frac{\pi_y}{1-\pi_y}\right) = \alpha_y - \theta_a \delta_{[a]} - \sum_{v=1}^4 \beta_{vj} \delta_{vj} - \lambda_{[time]}; \quad y = -1, 0, 1, 2, \dots, 27.$$

The additive covariate effects across all treatment arms for each patient are modeled through the  $\beta$  parameters. The  $\delta$  parameters are indicator functions for the treatment arm and covariate values for the baseline covariates. The efficacy of the treatment arms is modeled with the  $\theta$  parameters. The ordinal effect parameters ( $\alpha_y$ ) are modeled with a Dirichlet distribution with equal weight on each outcome and a sum of 1.

The baseline covariate effects are modeled with independent weak prior distributions:

$$\beta_{vj} \sim N(0, 10^2), \quad v = 1, \dots, 4; \quad j = 1, \dots, n_v.$$

The appropriate coefficients will be set to 0 within each covariate for identifiability (the goal will be the largest category set to 0).

The effects of time are adjusted within the model using two-week epochs and a smoothing model over time. The modeling of the time effects is set up with the most current period (2 epochs combined being the most recent month are set to 0):

$$\lambda_1 \equiv \lambda_2 \equiv 0$$

$$\lambda_2 - \lambda_1 \sim N(0, 0.15^2)$$

$$\lambda_T - 2\lambda_{T-1} + \lambda_{T-2} \sim N(0, \tau_\lambda^2); T \geq 3$$

$$\tau_\lambda^2 \sim IG(0.25, 0.00562)$$

The prior distributions for the mAB treatment effects are weak:

$$\theta_a \sim N(0, 10), a = 1, \dots, k.$$

## Arms

One of the treatment arms is selected as the referent arm for treatment effects and assigned a treatment effect of  $\theta_a = 0$ . The treatment arm at the first adaptive analysis with the largest sample size will be specified as the referent arm for the remainder of the trial.

## Model Convergence

Given the complexity of the model, conventions may be taken by the analysis team if there are convergence issues or model stability issues. For example, there may be outcome categories in the 30 possible primary outcome values (e.g., k number of hospital-free days, patient death) that do not occur. If this happens at analysis, the cells will be combined to achieve model convergence. For example, if the 4 hospital-free day outcome value does not occur it will be combined with 3, and so on, until every cell has occurred. Additional model stability conventions will be taken to preserve the model stability.

## Missing and Partial Data

If there are missing covariates for a patient in the as-infused patient population, the following conventions will be used.

1. If the treatment arm is missing the patient will be ignored.
2. If a baseline covariate is missing the referent value for that covariate will be used

For all model analyses, only patients who have achieved 28-days of follow-up from the date of the index infusion will be used in the analysis. No use or imputation of patient data for patients with less than 28 days will be conducted.

Given the EHR-based data summaries there will be no missing outcome data. If there is deemed to be a corrupted outcome that patient will be ignored. Some patients may have 28 hospitalization-free days that at subsequent analyses are found to have out of system hospitalizations. The data will be updated at future analyses.

## Trial Inferences

For the primary analysis, there is no “control” treatment and so all inferences are made comparing the individual treatment arms to each other. The main quantity of interest will be the relative odds ratio between any two treatments arms

$$OR_{ij} = \exp(\theta_i)/\exp(\theta_j).$$

The posterior probability that the odds ratio for arm  $i$  compared to arm  $j$  is greater than 1 (signifying that treatment  $i$  is superior to treatment  $j$ ) is used as a comparison between arms. Additionally, the posterior mean and 95% confidence interval between arms will be used to summarize relative treatment effects.

### Adaptive Design

The trial design is adaptive. A sequence of frequent interim analyses will be conducted as a function of enrollment rate. The expectation is to conduct monthly adaptive analyses. The following decision triggers will be addressed at each adaptive analysis:

**Arm Inferiority:** If one of the arms has a 99% chance of being inferior to any of the other available arms then the inferior arm will be declared inferior and may be removed from the trial. There may be conditions of the pandemic (e.g., variant frequency, new variants) or drug supply concerns that an arm is retained.

**Equivalence:** Any two arms in the trial may reach a declaration of equivalence. It is anticipated that no actions would take when equivalence is reached but a declaration and public disclosure may be made. There is a sliding scale of equivalence with different levels of equivalence bounds. A declaration of equivalence will be tied to the equivalence level. Equivalence with a bound of  $d$  is declared if the posterior probability of the odds ratio is with  $d$  is at least 95%:

$$\Pr\left(\frac{1}{1+\delta} \leq OR_{ij} \leq 1+\delta\right) \geq 0.95$$

The following levels are pre-defined:

1. The first level of equivalence occurs when there is 95% posterior probability that the odds-ratio is within a bound of  $d=0.25$
2. The second level of equivalence occurs when there is a 95% posterior probability that the odds-ratio is within a bound of  $d=0.20$
3. The third level of equivalence occurs when there is a 95% posterior probability that the odds-ratio is within a bound of  $d=0.15$
4. The fourth level of equivalence occurs when there is a 95% posterior probability that the odds-ratio is within a bound of  $d=0.10$
5. The fifth level of equivalence occurs when there is a 95% posterior probability that the odds-ratio is within a bound of  $d=0.05$

**Combination Futility:** When combinations of mAB are used the combination therapy may be compared to individual components of the combination. If there is more than a 95% probability that the effect of the combination mAB is no better than a 20% improvement in the odds ratio compared to each individual component then the combination may be declared *not clinically relevantly superior (futile)* to the individual components and the combination will be stopped. The comparison between a combination and the individual components will be declared when the combination is included within the platform trial.

**Trial Read-Outs:** There may be periodic “unblinding” of the trial results. When an arm is removed for inferiority or futility, the results for the inferior and the superior or the combination and its components of the two arms in the trigger will be unblinded and publicly released. The trial will continue and will utilize all data for any new inferences in the trial. Additionally, there may be need for periodic disclosure of the current trial results, such as when FDA revokes authorization for a given mAB. These disclosures will be made and the trial will continue unchanged.

**Response-Adaptive Randomization:** Assuming  $R$  arms available in the trial, response adaptive randomization will be utilized. The response adaptive randomization is conducted based on the probability that each arm has the optimal treatment effect (largest  $\theta$ ). Let  $q_a$  be the posterior probability that arm  $a$  is the optimal arm among the  $R$  arms in the randomization arm space:

$$q_a = \Pr(\theta_a = \max\{\theta_1, \dots, \theta_R\})$$

The randomization probabilities are weighted toward being equal to maintain sufficient randomization to each arm and because the assignment is open-label, to prevent any obvious patterns of assignments. The allocation probability for each arm is

$$\text{Allocation probability} = \frac{q_a + 1/R}{1+1}.$$

If an arm joins the trial and has no data on the primary endpoint, then the value of  $q_a$  for that arm is assigned to be  $1/R$  and the remaining arms probability of optimal summing to  $1 - \frac{1}{R}$ . This convention will create fixed randomization to a new arm in the trial until there is at least 1 observation of the primary endpoint for modeling.

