## Treatment Arms

There are two treatment arms that will be included in this analysis. The arms are:

1. C+I (casirivimab and imdevimab)
2. S (sotrovimab)

B+E (bamlanivimab and etesevimab) became available again at UPMC on September 16, 2021, due to a U.S. Government decision. However, only a small amount of patients received B+E from September 16 to September 29, 2021, relative to the much larger number that received C+I or S for the trial period of interest. Therefore, we have little belief a strong statistical conclusion for B+E exists. In addition, we continue to randomize into B+E. For these reasons, we will not analyze B+E in this readout.

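### Does the 99% inferiority trigger need a minimum amount of data before a small arm can have an established arm declared inferior?

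*SAP*

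**What the plan says.** The trigger in the SAP, Adaptive Design, applies "If one of the arms has a 99% chance of being inferior to any of the other available arms". The arm is then declared inferior, and it may be removed. Retention is allowed for pandemic conditions or drug supply. The same rule appears in both read-out appendices and in SAP version 1.1 within the combined document. Triggers are checked at every look: "The expectation is to conduct monthly adaptive analyses".

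No section sets a minimum arm size or event count. Four provisions come near:

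- Missing and Partial Data requires 28 days of follow-up, but for each patient, not for an arm.
- Response-Adaptive Randomization provides "fixed randomization to a new arm in the trial until there is at least 1 observation of the primary endpoint"; this governs allocation only.
- Model Convergence says "Additional model stability conventions will be taken to preserve the model stability", without a number.
- The October 28, 2021 read-out (Treatment Arms) left out B+E because "only a small amount of patients received B+E from September 16 to September 29, 2021" and "we have little belief a strong statistical conclusion for B+E exists". That was a judgement for one read-out.

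On the prior, Primary Analysis Model says "The prior distributions for the mAB treatment effects are weak" and gives N(0, 10). Public release is tied to removal ("When an arm is removed for inferiority or futility") and not to the declaration alone. The protocol (Data Monitoring) says that leadership receives the interim analyses to inform clinical policy.

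**The concern.** If every patient in a new arm has 28 HFD, the data cannot distinguish a moderate advantage from an enormous one. The likelihood is flat for large positive treatment effects, and a weak prior puts much of its mass there. The posterior probability that the new arm is better can then pass 99% on little information, and the arm declared inferior is the larger, better-measured one.

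The declaration is automatic, arms can join during the trial, and there is no target sample size, so small arms will occur. At stake is a false statement about a good arm, placed before the people who set policy. The prior notation adds doubt: the covariate prior, and the arm-mean prior in the subgroup model, are written with 10 squared, and the treatment prior with plain 10.

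**Working it through.** **Inputs.** From the SAP: threshold 0.99, prior N(0, 10), referent effect 0, monthly looks. The documents give no event rate, so p, the proportion with fewer than 28 HFD, is assumed to be 6, 12 or 20%. Accrual to the small arm is also assumed. The SAP states no operating characteristic for this trigger, so there is no figure to reproduce.

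**Event-free run.** In the proportional odds model, Pr(HFD = 28) = 1/(1 + exp(α27 − θ)), with α27 = logit(p) in the established arm. With n event-free patients the likelihood is L(θ) = [1/(1 + exp(α27 − θ))]^n, and the trigger fires when

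∫ over θ > 0 of L(θ)·prior(θ) ÷ ∫ over all θ of L(θ)·prior(θ) ≥ 0.99.

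Numerical integration, with the established rate taken as known, gives the smallest n. The chance of the run between identical arms is (1 − p)^n.

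| Prior reading | p | n | Expected events np | (1 − p)^n |
|---|---|---|---|---|
| Variance 10 | 6% | 41 | 2.46 | 0.94^41 = 7.9% |
| Variance 10 | 12% | 20 | 2.40 | 0.88^20 = 7.8% |
| Variance 10 | 20% | 12 | 2.40 | 0.80^12 = 6.9% |
| SD 10 | 6% | 24 | 1.44 | 0.94^24 = 22.7% |
| SD 10 | 12% | 12 | 1.44 | 0.88^12 = 21.6% |
| SD 10 | 20% | 7 | 1.40 | 0.80^7 = 21.0% |

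The prior therefore acts as a floor: below these sizes the trigger cannot fire against the established arm. Estimating the established arm from 200 or 1,000 patients moves n by at most 3 (checked at p = 5 to 20%). Above the floor the one-look rate falls, unevenly. At p = 10% and variance 10 it is 7.2% at n = 25, 3.4% at 50, 2.4% at 100 and 1.5% at 400.

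**What a minimum would do.** Take 6 expected events in the smaller arm: 6/0.06 = 100, 6/0.12 = 50 or 6/0.20 = 30 patients. Documented periods are short: bamlanivimab alone ran March 10 to 31, the read-out windows were March 10 to June 25 and July 14 to September 29, and opening to the last SAP date is about 8 months. Repeated looks over such lengths (variance 10, HFD 28 versus fewer, first look at a random point in the month) give these chances of declaring the established arm inferior, without → with the minimum:

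| p | Outcomes/month | Looks | Identical arms | True OR 2 | True OR 3 |
|---|---|---|---|---|---|
| 6% | 10 | 8 | 6.3 → 0% | 25.1 → 0% | 40.4 → 0% |
| 6% | 20 | 4 | 4.8 → 0% | 21.4 → 0% | 36.1 → 0% |
| 12% | 10 | 4 | 4.9 → 0% | – | 35.4 → 0% |
| 12% | 20 | 3 | 4.4 → 1.0% | – | 48.7 → 24.2% |

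The zeros do not depend on the prior. In the first two rows the arm has at most 80 patients, and 80 × 0.06 = 4.8, which is below 6. In the third, 40 × 0.12 = 4.8. Over the wider set of slow settings (3 to 8 looks, 6 or 12%, odds ratio 2 or 3) the loss of correct declarations is about 7 to 40 points and the gain about 3 to 6 points.

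**Faster accrual.** At 60 to 180 outcomes per month over four looks, false declarations are 3.4 to 5.0% without the minimum and 2.9 to 3.6% with it (variance 10). Event-free runs are the first trigger in only 0.2 to 2.1 points. The rest comes from repeated looks, which a minimum does not address.

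**Which accrual is likelier.** The documents give no accrual by arm. If the 1,935 patients in the baseline table are the treated group for March 10 to June 25 (its column headings are not visible), that is 1,935/108 × 30, or about 540 per 30 days. The allocation formula (q + 1/R)/2 cannot fall below 1/(2R). With three arms that is 1/6, or about 90 per month. Shortages could lower this.

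**The case for a change.** The case for a written minimum is respectable. The gap is real, the declaration is automatic, and the retention clause does not mention sparse data. An event-free arm need not cause a convergence failure, because the prior is proper, so the stability clause may never come into play. The B+E decision shows that the sponsor shares the caution but applied it by judgement. A one-directional minimum would not delay signals against the small arm. Over a long horizon it also looks cheap: at 6% events, 10 per month and 20 looks, with a true odds ratio of 2, correct declarations fall only from 57.0 to 50.9%, a loss of 6.1 points. If 10 is a standard deviation the benefit is larger: 9.9 to 20.5% false declarations without the minimum and 4.3 to 6.5% with it in slow arms.

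The textual points stand. The cost argument does not, because 20 looks at 10 per month is 20 months, against about 8 months from opening to the last SAP date. Over realistic lengths the minimum mostly switches the trigger off in slow arms. The standard-deviation reading is the less likely one, since the SAP writes its other normal priors as squared standard deviations. A slip for 10 squared cannot be excluded from the text, but the analysts who fit the model know which value they use.

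**Conclusion.** No change to the plan follows. The trigger can fire on an event-free run worth about 2.4 expected events (variance 10) or 1.4 (SD 10), with a chance between identical arms of about 7 to 8% or 21 to 23% at that run length. That is a property of a weak prior, and the SAP promises no frequentist error rate that it breaches. Removal is discretionary, release follows removal, and the one sparse arm on record was set aside sensibly.

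A minimum of 6 expected events exchanges roughly 3 to 6 points of false declarations for roughly 7 to 40 points of correct ones in slow arms, and brings only about 1 to 2 points at 60 or more outcomes per month. Statisticians could reasonably choose either side. The variance-or-SD notation is a missing detail, not a design fault.

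These sizes rest on assumed event rates and accrual, a known rate in the established arm, and no covariate or time effects. The repeated-look tables use variance 10. A persistently slow arm kept open well beyond the documented periods would make a minimum cheaper and the case for it stronger.

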### **Modeling Treatment Heterogeneity**

During the course of the trial, and during a trial read-out, inferences of relative treatment effect by different subgroups may be utilized. In these cases, the treatment effect is modeled as a function of subgroup within the single larger model. Each level of the subgroup will be identified and added as a covariate in the model and then the treatment effect,  $\theta_{as}$ , will be modeled separately within each subgroup,  $s = 1, \dots, S$ , as  $\theta_{a1}, \theta_{a2}, \dots, \theta_{aS}$ , with hierarchical prior distribution:

$$\theta_{as} \sim N(\mu_a, \tau_a^2), a = 1, \dots, k; s = 1, \dots, S.$$

$$\mu_a \sim N(0, 10^2); \tau_a^2 \sim IG(0.25, 0.1).$$

### **Assessment of COVID-19 Variants**

The COVID-19 variant type is a predefined subgroup for analysis. The variant type for each patient is unknown at baseline, but samples will be collected and reported upon sequencing. The posterior median odds ratios and 95% credible intervals will be reported for each arm comparison within each variant subset. In addition, because a large percentage of mAB infused patients will not have variant sequencing data (at least in near real time), a second “surrogate” approach will be used to compare the relative efficacy of the mAB regimens in the full treated population over time and by variant type.

Using Pennsylvania statewide data, we will estimate the prevalence of a given variant type by time. Then, we can categorize patients into various time epochs relative to the variant prevalence. These categories will be provided based upon the changing distributions over time in our region.

To consider the internal validity of this “surrogate” approach, we will use data from the subset of patients with actual genotype sequencing, compare the proportion of patients with prevalence of the variant type of interest across levels of the surrogate classification (i.e., Cochran Mantel-Haenszel test of trend).

### **Adaptive Analyses Reporting**

The primary analysis will read out with summaries of the potential arm triggers for each arm actively in the “regimen space.” These summaries will include the probability each mAB is optimal in the active regimen space and the randomization probabilities.

A second analysis will be conducted with all arms (even those closed) in the regimen space, to report the probability each regimen is optimal among the larger regimen space.

As the EHR system contains the same covariate and baseline data for both mAB treated and untreated patients, we have continuously updated flags for each patient in the system as being “mAB eligible” (or not) based on EUA criteria on the date the patient became COVID-19 positive. With appropriate selection, this affords 2 untreated control groups for analysis that we will describe using mean (SD), median [IQR], and proportions, as appropriate: mAB eligible patients who were never randomly assigned to a respective mAB regimen, and mAB eligible patients who were randomly assigned to a mAB regimen yet did not receive treatment.

